3.3 Treatment

Roflumilast cream 0.15% or vehicle cream will be administered QD for 28 days (+/- 3 days).

- Roflumilast cream 0.15%
- Vehicle cream

3.4 Randomization, Replacement, and Unblinding Procedures

Randomization will take place at the Baseline visit prior to first dosing. Subjects who meet all eligibility criteria will be randomized at a 2:1 ratio (drug:vehicle) to receive Roflumilast cream 0.15% QD or matching vehicle QD. The randomization will be stratified by vIGA-AD score at baseline ('Mild' vs. 'Moderate') and by study site according to a computer-generated randomization list. Kits containing tubes of study medication will be assigned to each subject using an internet-based response system (IWRS). A subject may receive more than one kit for the treatment period. The kits and tubes are blinded and each kit is numbered with a unique kit number.

The study is double-blinded, therefore neither the subjects nor the Investigator, sponsor and clinical personnel will be aware of which treatment an individual subject receives.

	STATISTICAL ANALYSIS PLAN, Version 1.0
Protocol Number: ARQ-151-312	Sponsor: Arcutis Biotherapeutics, Inc.

3.5 Changes to the Analysis from the Protocol

Rationale for change	Description of the change
A categorical summary was excluded from the SAP as it was determined that it	Original text: The amount of investigational product used by
was not necessary.	each subject based on tube weight will be summarized by treatment using descriptive statistics, and categorically.
	Changed to:
	The amount of investigational product used by
	each subject based on tube weight will be summarized by treatment using descriptive
	statistics.
To separate COVID patient from Per Protocol analysis set.	Original text: Per protocol (PP) population will include all subjects in the ITT population, who are at least 80% compliant with study medication application, and show no major deviations from the study protocol that would affect the interpretation of efficacy. In addition, subjects who miss the Week 4 vIGA-AD assessment specifically due to novel coronavirus disease-19 (COVID-19) disruptions will be excluded from per protocol population. Changed to: Per protocol population will include all subjects
	who are randomized, at least 80% compliant with study medication application, have a vIGA-AD assessment within the Week 4 visit window, and show no "major deviations" from the study protocol that would affect the interpretation of efficacy.
Added mITT population to address	The mITT population includes all randomized
COVID-19 impact.	subjects with the exception of subjects who missed the week 4 vIGA-AD assessment specifically due to COVID-19 disruption. This population will be used for sensitivity analysis for the primary endpoint.

	STATISTICAL ANALYSIS PLAN, Version 1.0
Protocol Number: ARQ-151-312	Sponsor: Arcutis Biotherapeutics, Inc.

4 POPULATIONS FOR ANALYSIS

4.1 Intent-to-Treat (ITT) Population

Intent-to-Treat population will include all subjects who are randomized, and all subjects will be analyzed according to the treatment group and stratum to which they were randomized.

4.2 Modified Intent-to-Treat (mITT) Population

The mITT population includes all randomized subjects with the exception of subjects who missed the week 4 vIGA-AD assessment specifically due to COVID-19 disruption. This population will be used for sensitivity analysis for the primary endpoint. All subjects will be analyzed according to the treatment group and stratum to which they were randomized.

4.3 Per Protocol (PP) Population

Per protocol population will include all subjects who are randomized, at least 80% compliant with study medication application, have a vIGA-AD assessment within the Week 4 visit window and show no "major deviations" from the study protocol that would affect the interpretation of efficacy. A complete list of major deviations from the study protocol will be created prior to unblinding and include a list of all subjects who will be excluded due to those major deviations. See section 7.2 for more details.

All subjects will be analyzed according to the actual treatment group they received and the stratum they belong to. Actual and randomized treatment will only differ if the subject received the wrong treatment throughout their participation in the study.

4.4 vIGA-AD Moderate ITT Population

vIGA-AD Moderate ITT population will be a subset of the ITT population with vIGA-AD score (randomized score) 'Moderate' at randomization.

All subjects will be analyzed according to the treatment group and the stratum to which they were randomized.

4.5 vIGA-AD Moderate PP Population

vIGA-AD Moderate PP population will be a subset of the PP population with vIGA-AD score (actual score) 'Moderate' at randomization.

	STATISTICAL ANALYSIS PLAN, Version 1.0
Protocol Number: ARQ-151-312	Sponsor: Arcutis Biotherapeutics, Inc.

All subjects will be analyzed according to the actual treatment group they received and the stratum they belong to. Actual and randomized treatment will only differ if the subject received the wrong treatment throughout their participation in the study.

4.6 WI-NRS Population

WI-NRS population will be a subset of the ITT population among subjects ≥ 12 years old with average weekly baseline WI-NRS score ≥ 4 .

The subjects in WI-NRS population are those:

- 1. Completed at least 4 of 7 evaluable daily WI-NRS questionnaires during the last 7 days of the Screening period;
- 2. Have a mean baseline WI-NRS score ≥ 4.0, defined as the average of all non-missing scores reported during the last 7 days of the Screening period if at least 4 of 7 evaluable daily WINRS questionnaires available. If 4 or more evaluable daily questionnaires are missing, then the data will be treated as missing.

All subjects will be analyzed according to the treatment group and stratum to which they were randomized.

4.7 Safety Population

Safety population will include all subjects who are enrolled and received at least one confirmed dose of study medication.

Subjects will be analyzed based on the treatment group received and the stratum they belong to. Actual and randomized treatment will only differ if the subject received the wrong treatment throughout their participation in the study.

4.8 Pharmacokinetic (PK) Population

Pharmacokinetic population will include all subjects receiving the active drug with quantifiable plasma concentrations of roflumilast.

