5.3.4. Pharmacokinetics Assessment

PK draws will be performed according to the Schedule of Visits and Assessments (Section 1.3) for all subjects at all sites:

• A single PK assessment (trough) will be performed in all subjects with a blood sample collected at Week 4/Day 29.

Ensure study medication is not applied in the area where PK will be drawn.

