- h Adolescents and adults will complete the C-SSRS (12 years of age and older). Adults will complete the PHQ-8. Adolescents (ages 12 to 17, inclusive) will complete the PHQ-A (PHQ-9 modified). Parents/caregivers will complete CDI-2 (parent report) for children 6-11 years of age, inclusive.
- The DLQI will be completed by subjects ≥17 years of age. The CDLQI will be completed for subjects 6 to 16 years old, inclusive. The Dermatitis Family Impact Questionnaire (DFI) will be completed by parents/caregivers for all subjects 6 to ≤17 years of age.
- ^j Photography of AD lesion(s) selected by the Investigator will be performed at all investigational sites. All efforts will be made to de-identify the subjects. Canfield equipment will be used to capture photographs. Subjects who are unwilling to participate in the medical photography will be allowed to opt out of this procedure, as documented on the Informed Consent Form.

	STATISTICAL ANALYSIS PLAN, Version 1.0
Protocol Number: ARQ-151-312	Sponsor: Arcutis Biotherapeutics, Inc.

- ^k A urine pregnancy test will be administered to all females of child-bearing potential. A negative result is required for continued participation in the study, and results must be available prior to dispensing of study drug at each visit.
- ¹ For all subjects entering this study under Amendment 2, a single PK trough draw will be collected at Day 29 only for subjects ≥12 years old. Ensure study medication was not applied in the area where PK will be drawn.
- ^m Subjects to apply assigned IP during clinic visits, except for the Day 29/ET visit.
- ⁿ It is expected that kits will be dispensed based on %BSA affected. See IP Handling Manual for details.
- On Day 8 and 15, dispensing of IP is optional. Site should review IP kit to ensure sufficient IP is available until the next visit and only dispense additional IP if needed. On Day 29, if the subject is unable to perform the Day 29 clinic visit due to COVID-19 restrictions (isolation, quarantine, etc.) then additional IP may need to be dispensed so IP can continue to be applied at home until the subject is able to return to the clinic to complete the Day 29 assessments (see IP Handling Manual for the process to dispense additional IP at or after Day 29).
- P Every tube should be weighed and recorded when dispensed and returned. See IP Handling Manual for details.
- ^q Compliance determination is described in the IP Handling Manual

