5.4 Windowing Conventions

Visits will be analysed as scheduled. Unscheduled, early termination visits, and/or retest measurements will only be included if a scheduled measurement is not available and the early termination or unscheduled/retest measurement falls within the analysis visit windows as described in Table 2, Table 3, and Table 4 when appropriate. Unscheduled/retest measurements will be listed.

If there is more than one assessment for a given timepoint and analysis visit when a scheduled measurement is not available, the assessment closest to the target day will be considered.

Table 2 Analysis Visit Windows for Efficacy Endpoints, Vital Signs, CDI-2, PHQ-8, PHQ-A, C-SSRS and Local Tolerability Assessment

Analysis Visit	Target Day	Lower Limit	Upper Limit
Week 1	8	2	11
Week 2	15	12	22
Week 4	29	23	43

	STATISTICAL ANALYSIS PLAN, Version 1.0
Protocol Number: ARQ-151-312	Sponsor: Arcutis Biotherapeutics, Inc.

Table 3 Analysis Visit Windows for Clinical Laboratory, Physical Examination and PK assessment

Analysis Visit	Target Day	Lower Limit	Upper Limit
Week 4	29	23	43

Table 4 Windows for the derivation of Average Weekly WI-NRS

Days for calculation of weekly average	Week (Derived)
(-7, -1)*	Baseline
(1, 7)	Week 1
(8, 14)	Week 2
(15, 21)	Week 3
(22, 28)	Week 4

^{*} Day 1 WI-NRS score will be used to calculate the value for week 1 only when it is collected after the application of the first first study drug. If Day 1 WI-NRS score is collected prior to or concurrently with the application of the first study drug, then the Day 1 WI-NRS score will be included in baseline calculation.

Note: With the following caveat, if more than one WI-NRS score is available on the same day, the worst score of the day will be considered in the analyses. The caveat is that if a subject has two WI-NRS assessments on Day 1 and one of them was collected before the first study treatment dosing while the other one was collected after the first study drug dosing. Under such circumstances, the assessment collected before the first study drug dosing will be considered for the Baseline analysis visit while the assessment collected after the first study drug dosing will be considered for the Week 1 analysis visit.

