5.8 Handling of Retests, Unscheduled Visits, and Early Termination Data

Retests measurements, Unscheduled measurements, and ET visit assessments will be included in analysis and be summarized via analysis visit windowing according to the windowing conventions in section 5.4.

All data from retest, unscheduled measurements and ET visit assessments will be listed.

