7 STUDY SUBJECTS

7.1 Disposition of Subjects

All subjects who provide informed consent will be accounted for in this study. The number of subjects who were screened and who failed screening (screen failures) will be presented. The reasons for screen failure will be presented for all screened subjects who failed screening.

The number of subjects randomized will be presented by treatment group. The number and percentage of the subjects included in each analysis population will be provided by treatment group. The number and percentage of the subjects who completed the study, who discontinued the study, the reasons for study discontinuation, and early termination due to COVID-19 disruption will be presented by treatment group. The percentages will be calculated using the number of the randomized subjects as denominator.

Number of days in the study will be summarized with descriptive statistics by treatment group and overall. For each subject, the number of days in the study will be calculated as following:

Number of days in study = Date of completion/discontinuation -1^{st} dose date +1

	STATISTICAL ANALYSIS PLAN, Version 1.0
Protocol Number: ARQ-151-312	Sponsor: Arcutis Biotherapeutics, Inc.

A listing of subject's disposition and randomization will be provided. Information on first screening for subjects who were rescreened, including the rescreened subject identifier and the reason for first screening failure, will be presented under the first screening subject identifier. The reason for screening failure will be listed as well.

A table of randomized strata vs. actual strata will be provided if there is any mis-randomization discrepancy.

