14 PHARMACOKINETICS ANALYSIS

Concentration data will be summarized by visit by age group (<18 vs. >=18) and overall, for active treatment group using descriptive statistics, reporting n, mean, standard deviation, median, Q1, Q3, minimum, and maximum, and geometric statistics including geometric mean and coefficient of variation. For computation of mean plasma concentrations, data that are below the limit of quantification (BLQ) will be set to 0.0001. The PK population will be used for these analyses.

PK data will be presented in the listing.

	STATISTICAL ANALYSIS PLAN, Version 1.0
Protocol Number: ARQ-151-312	Sponsor: Arcutis Biotherapeutics, Inc.

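### SAP 4.8 admits only subjects with quantifiable roflumilast to the PK population, so any on-treatment trough below the assay limit ordinarily drops out and the roflumilast summaries are biased upward; low priority

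*SAP*

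**What the plan says.** SAP 4.8 defines the population: "Pharmacokinetic population will include all subjects receiving the active drug with quantifiable plasma concentrations of roflumilast". Protocol 6.3, in the supplied original version, has the same definition. The SAP is written to protocol Amendment 3, which was not supplied.

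Protocol 5.3.4 schedules one draw: "A single PK assessment (trough) will be performed in all subjects with a blood sample collected at Week 4/Day 29". The PK footnote in SAP 3.2 narrows this for subjects entering under Amendment 2: "a single PK trough draw will be collected at Day 29 only for subjects ≥12 years old". The draw sits in the combined Day 29/early-termination column, and SAP 5.4 (Table 3) gives Week 4 PK a window of Days 23 to 43.

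SAP 14 summarises concentrations by age group (under 18, 18 and over) and overall, with arithmetic and geometric statistics. For computing mean concentrations it adds: "data that are below the limit of quantification (BLQ) will be set to 0.0001. The PK population will be used for these analyses". It gives no unit for 0.0001, no link to the assay limit, and no statement on whether the rule covers the geometric mean and CV.

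**The concern.** Membership of the population depends on the variable being summarised. The PK objective in SAP 2 is systemic exposure to roflumilast and its N-oxide after four weeks of daily application, not exposure among subjects whose roflumilast happened to be measurable. Removing the lowest values raises every measure of location and shrinks the spread. If BLQ rates differ by age, the comparison of the two age groups is distorted as well.

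The two sections also fit poorly together. SAP 14 sets a rule for BLQ data inside a population that SAP 4.8 has ordinarily cleared of BLQ roflumilast values. The analytes are then handled differently without explanation: a BLQ roflumilast result excludes the subject, while a BLQ N-oxide result stays in at 0.0001.

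**Working it through.** **Does a BLQ trough remove the subject?** One sample is scheduled. If it is BLQ for roflumilast, the subject has no quantifiable roflumilast and fails SAP 4.8. The exception is a subject with a second, quantifiable sample. SAP 5.8 says "Retests measurements, Unscheduled measurements, and ET visit assessments will be included in analysis and be summarized via analysis visit windowing", but SAP 5.4 says "retest measurements will only be included if a scheduled measurement is not available", so the scheduled BLQ value would appear to be the one kept. The case should be rare, since the unscheduled-visit list in protocol 5.6 has no PK draw. Hence *ordinarily*.

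**Direction for roflumilast.** This is left truncation. For any distribution with some probability below the limit, the mean of the values above it exceeds the overall mean. The same holds on the log scale, and quantiles shift upward.

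**Size.** The plan states no PK figure, so there is nothing to reproduce. Assumptions, not document figures: log-normal concentrations with log SD s of 1.0 or 1.5, and BLQ share f. Let z = probit(f) and λ = φ(z)/(1−f). Ratios of quantifiable-only to all samples:

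- mean: [1−Φ(z−s)]/(1−f)
- geometric mean: exp(sλ)
- p-quantile: exp{s[probit(f+(1−f)p)−probit(p)]}
- truncated log SD: s√(1+zλ−λ²); geometric CV: √(exp(SD²)−1)

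At f = 0.05, z = −1.645 and λ = 0.1086. For s = 1.0 the mean ratio is [1−Φ(−2.645)]/0.95 = 1.048 and the geometric mean ratio is exp(0.1086) = 1.115.

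| f = 0.05 | s = 1.0 | s = 1.5 |
|---|---|---|
| Mean | 1.048 | 1.052 |
| Geometric mean | 1.115 | 1.177 |
| Median | 1.065 | 1.099 |
| Lower quartile | 1.121 | 1.186 |
| Upper quartile | 1.041 | 1.062 |
| Geometric CV | 131% to 112% | 291% to 228% |

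At f = 0.01 the mean ratio is 1.010 for both values of s, and the geometric mean ratio is 1.027 and 1.041. Solving exp(sλ) = 1.10 gives f = 4.3% (s = 1.0) or 2.7% (s = 1.5) as the BLQ share at which the geometric mean is overstated by 10%.

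**N-oxide.** Two effects oppose each other. Selection on quantifiable roflumilast pushes the N-oxide summary up if the analytes are positively correlated: with joint log-normality, correlation 0.5, s = 1.0 and 5% roflumilast BLQ, the geometric mean ratio is exp(0.5 × 0.1086) = 1.056 before any N-oxide substitution. BLQ N-oxide values set to 0.0001 push it down. With 1% roflumilast BLQ, 5% N-oxide BLQ, log SD 1.0, correlation 0.5 to 0.8, 0.0001 at one tenth of the limit and the rule applied to geometric statistics, the N-oxide geometric mean is 6 to 7% too low.

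**Why widening the population is not enough.** If BLQ values are kept and set to k times the assay limit, the geometric mean ratio is exp{(1−f)sλ + f(ln k + sz)}. Changes at f = 0.05:

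| k | s = 1.0 | s = 1.5 |
|---|---|---|
| 1/2 | −1.4% | −0.3% |
| 1/10 | −9.0% | −8.0% |
| 1/100 | −18.9% | −18.0% |

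**The case against.** **Disclosure.** A reader might infer that BLQ subjects disappear from view. They do not. SAP 7.1 says "The number and percentage of the subjects included in each analysis population will be provided by treatment group", SAP 8 lists population flags, and SAP 14 says "PK data will be presented in the listing". This stands, but listings do not correct the summary tables. The count alone cannot show BLQ either, because it also falls for missed draws and for subjects aged 6 to 11 who are not sampled under Amendment 2.

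**Off-treatment samples.** Protocol 4.8.6 and 4.8.7 separate stopping treatment from leaving the study, and draws may come at early termination or up to Day 43. A BLQ value from someone no longer applying drug does not represent exposure after four weeks of application, and leaving it out need not bias that target. This stands, and it limits the point to on-treatment samples.

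**The BLQ rule is not idle.** It acts on the N-oxide, and a small non-zero value can be logged. Both are true. Which statistics it covers is still unstated.

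**Materiality.** No BLQ rate is given, and the results of the earlier PK studies are not in the supplied text. Protocol 2.4.2 suggests topical dosing may lack peak-to-trough variation, which does not point to frequent BLQ troughs, though it does not exclude them. No decision rule uses the PK summaries, and overstated exposure is the cautious direction for safety. All of this stands and lowers the priority.

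**Conclusion.** The point holds for roflumilast. If any on-treatment active-arm sample is BLQ, its subject is ordinarily dropped, and the summarised mean, geometric mean, median and quartiles are biased upward relative to all sampled on-treatment subjects. That direction needs no distributional assumption. The size cannot be derived from the documents: it is zero with no BLQ samples, and the percentages above rest on an assumed BLQ share and log SD.

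A reader might infer that all summarised exposure is overstated. The documents do not support that: N-oxide values below the limit stay in at 0.0001 and can pull that summary down, so its net direction is open. Nor do they show that the roflumilast overstatement is material. PK is descriptive and efficacy inference is untouched, so this is a low-priority correction that is worth making because it is cheap.

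**What to change.** - **SAP 4.8:** define the PK population as all active-treated subjects with an evaluable Week 4 PK sample, quantifiable or not. Define evaluable without reference to the measured concentration, for example a sample within the analysis window, with a prespecified rule for early-termination or off-treatment draws based on the recorded last application.
- **SAP 14, counts:** report n (%) BLQ by analyte and age group.
- **SAP 14, BLQ rule, at the same time:** state which statistics it covers. For geometric statistics, replace 0.0001 with a prespecified value or method tied to the assay limit; half the lower limit of quantification is one option.
- **SAP 3.5:** record the change if Amendment 3 carries the same definition.

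The cost is a few sentences in SAP 4.8 and 14, at most one row in SAP 3.5, and no new samples. The downside is that reported average roflumilast exposure becomes lower if any samples are BLQ, by an amount that depends on the BLQ rate.

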5 GENERAL CONSIDERATIONS

Formats and layouts of tables, listings, and figures (TLF) will be provided in a separate document (output general layout is described in Appendices

Appendix 1).

	STATISTICAL ANALYSIS PLAN, Version 1.0
Protocol Number: ARQ-151-312	Sponsor: Arcutis Biotherapeutics, Inc.

5.1 Sample Size

There are approximately 650 subjects planned for this study. In order to have the desired power for the secondary endpoint of vIGA-AD Success in subjects with a vIGA-AD score of 'Moderate' at randomization, approximately 490 of the subjects to be accrued will have vIGA-AD score of 'Moderate' at randomization. Randomization will be stratified by vIGA-AD score ('Mild' vs. 'Moderate') and by study site.

The sample size of 650 subjects provides approximately 95% power to detect an overall 15% difference (Odds Ratio = 2.1) between treatment groups on vIGA-AD success at Week 4 at α =0.05 using a 2-sided stratified Cochran-Mantel-Haenszel (CMH) test. The results from a recent Phase 2 study (ARQ-151-212) of Roflumilast cream 0.15% compared to vehicle treatment were used to estimate the treatment difference. Specifically, in the Phase 2 trial, approximately 37% of subjects demonstrated vIGA-AD Success at Week 4 in the ARQ-151 0.15% group compared to 22% in the vehicle group. The sample size of 490 also provides approximately 90% power to detect an overall 17% difference (Odds Ratio = 2.1) between treatment groups (28% of vIGA-AD Success at Week 4 in vehicle treatment) on vIGA-AD Success at Week 4 among subjects with vIGA-AD score 'moderate' at randomization. The same testing method, the stratified CMH test, will be used as for the primary endpoint.

To control for familywise type I error at level of 0.05, the secondary endpoint of vIGA-AD Success at Week 4 in subjects with vIGA-AD of 'Moderate' at randomization will only be tested if the primary endpoint demonstrates statistical significance. In addition, the remaining secondary endpoints will be inferentially tested only if the primary and secondary endpoint (vIGA-AD Success at Week 4 for subjects with vIGA-AD score of 'Moderate' at randomization) comparisons are statistically significant using the hierarchical testing procedure by partitioning of alpha (see Section 6.5 for more details).

